
2 ANALYSIS COHORT DEFINITIONS

Since enrollment is concurrent with receiving the first study vaccination, all participants will provide some safety data. However, for immunogenicity analyses, it is possible that data may be missing for various reasons, such as participants terminating from the study early, problems in shipping specimens, low cell viability of processed peripheral blood mononuclear cells (PBMCs), or high assay background. Immunogenicity data from 17 phase 1 and 2 phase 2a HVTN vaccine trials, which began enrolling after June 2005 (data as of September 2014), indicate that 15% is a reasonable estimate for the rate of missing data at month 6.5. For this reason, sample size calculations account for 15 enrolled participants on each of the vaccine groups having missing data for the primary immunogenicity endpoints.

3 POTENTIAL CONFOUNDERS

Characterization of the safety of the vaccine is susceptible to confounding by adverse events not related to the vaccine that by chance occur more often in one arm of the trial than another. Therefore analyses involving adverse events will incorporate the reported relationship to product as assessed by the site clinician.

4 STATISTICAL ANALYSIS

This section describes the final study analysis, unblinded as to treatment group assignment. All data from enrolled participants will be analyzed according to the initial randomization assignment regardless of how many vaccinations they received. In the rare instance that a participant were to receive the wrong treatment at a vaccination time, a decision will be made as to how to report their safety data based on the nature of the wrong treatment and the number of correct and incorrect study injections the participant received; a revised SAP would document such a decision. Analyses are modified intent-to-treat in that individuals who are randomized but not enrolled do not contribute data and hence are excluded. Because of blinding and the brief length of time between randomization and enrollment—typically no more than 4 working days—very few such individuals are expected.

Analyses for primary endpoints will be performed using SAS and R. All other descriptive and inferential statistical analyses will be performed using SAS, StatXact, or R statistical software.

No formal multiple comparison adjustments will be employed for multiple safety endpoints, multiple primary immunogenicity endpoints, or secondary endpoints. However, multiplicity adjustments will be made for certain immunogenicity assays, as specified in the SAP, when the assay endpoint is viewed as a collection of hypotheses (e.g., testing multiple peptide pools to determine a positive response).

Immunogenicity data from this study may be combined with other phase 1/2a studies within the P5 partnership HIV vaccine program. Comparable eligibility criteria and validated assays for primary immunogenicity endpoints will be used to mitigate the potential bias introduced by combining data across studies conducted over an extended period of time.

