4.4 Immunogenicity Analysis

4.4.1 General approach

For the statistical analysis of immunogenicity endpoints, data from enrolled participants will be used according to the initial randomization assignment regardless of how many injections they received. Additional analyses may be performed, limited to participants who received all scheduled injections per protocol. Assay results that are unreliable, from specimens collected outside of the visit window, or from HIV-infected participants after infection are excluded. Since the exact date of HIV infection is unknown, any assay data from blood draws 4 weeks prior to an infected participant's last seronegative sample and thereafter may be excluded. If an HIV-infected participant does not have a seronegative sample after enrollment, then all data from that participant may be excluded from the analysis.

Response rates will be analyzed by tabulating the frequency of positive response for each endpoint and treatment group at each timepoint for which an assessment is performed. For CD4+

and CD8+ T-cell response, response rates to the individual peptide pools will also be calculated. Crude response rates will be presented with their corresponding 95% confidence interval estimate calculated using the score test method [1]. For the primary endpoints of CD4+ T-cell response rates for TV1 and 1086, differences between groups will be tested with a 2-sided Barnard's exact test at an alpha level of 0.05. For secondary and exploratory assay endpoints, response rates and 95% confidence intervals will be calculated if appropriate for the endpoint. No adjustment will be made to the vaccine group estimates for the false positive rates in the placebo group.

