6 IMMUNOGENICITY TABLES AND FIGURES, BY ASSAY

6.1 Intracellular Cytokine Staining

Flow cytometry will be used to examine vaccine specific CD4+ and CD8+ T cell responses following stimulation of PBMCs with synthetic HIV peptides that span the proteins encoded by the vaccine. Vaccine specific T-cell response magnitudes and response rates will be assessed at the Month 6.5 timepoint/Visit 10 (2 weeks after the fourth vaccination) and the Month 12 timepoint/Visit 12 (6 months after the fourth vaccination). Visit 10 analyses will be conducted first. Afterwards Visit 12 analyses will be conducted and combined with the Visit 10 analyses, once Visit 12 specimens become available. Contingent on the results of the Visit 10 and Visit 12 analyses, additional reports may be generated for Visit 7. The following peptide pools will be used:

Peptide Pool	Pool ID	Lot Number
LAI-Gag	PP500025	11S227
LAI gp41 TM	PP502556	15H008AB
Env-1-ZM96	PP502442	14C093A
Env-2-ZM96	PP502446	14C097A
TV1 gp120	PP502557	15H020A
1086 gp120	PP502551	15H015A

The following functional markers will be measured from a 17-colormetric panel: AViD, CCR7, CD14, CD56, CD45RA, CXCR5, ICOS (CD278), PD-1 (CD279), CD3, CD4, CD8, CD154, IFN- γ , Granzyme B, IL-2, IL-4, IL-17a, and TNF α . The initial reports will present IL-2 and IFN- γ responses. Subsequent reports may be produced to include data from the other functional markers.

All analyses are performed on LAI-Gag, LAI-Gag gp41 TM, Env-1-ZM96, Env-2-ZM96, TV1 gp120 Env, and 1086 gp120 Env, individually and according to 2 levels of pooling:

1. Env-ZM96: Sum of Env-1-ZM96 and Env-2-ZM96
2. Any Env: the maximum of Env ZM96, 1086 gp120, and TV1 gp120, where Env ZM96 is the sum of Env-1-ZM96 and Env-2-ZM96; 3

3. Any HIV: the sum of Any Env, LAI-Gag gp 41 TM and LAI-Gag.

Positivity calls and subsequent analyses are performed separately for CD4+ and CD8+ T cell responses. Fisher's exact test criteria will be used for positivity calls before assays on all samples are complete. After, MIMOSA criteria will be used for positivity calls. If at least one peptide pool for a specific HIV-1 gene is positive, then the overall response to the gene is considered positive. If any peptide pool is positive, then the overall response to HIV-1 (Any HIV) for that T-cell subset is considered positive.

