Positive response rates are compared between treatment groups using Barnard's exact test. Response magnitudes are compared between treatment groups using Wilcoxon rank sum test. Positive response rates are compared within treatment group, across timepoints using McNemar's test. Response magnitudes are compared within treatment group, across timepoints using the Wilcoxon signed rank test. Statistical tests with an unadjusted p-value ≤ 0.05 will be considered statistically significant.

The following comparisons of the immune response rate and magnitude will be performed:

- Pairwise comparisons of response rates and response magnitudes between all treatment groups.
- Pairwise comparisons of response rates and response magnitudes within treatment group, between the Visit 10 and Visit 12 timepoints.
- If additional assays are performed at Visit 7, then between time point comparisons, within treatment group, will be performed between Visit 7 and Visit 10 and between Visit 7 and Visit 12.

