6.1.1 List of Tables

- Response rate table by lab, T cell subset, peptide pool, visit, day, and group/treatment arm for cells expressing either IL-2 and/or IFN- γ using Fisher's exact test criteria and/or MIMOSA criteria.
- Summary statistics (i.e., min, mean, median, max) of response magnitudes among responders for T-cell subset, peptide pool, visit, and group/treatment arm.
- Summary statistics (i.e., min, mean, median, max) of response magnitudes among all participants (positive and negative responders) for T-cell subset, peptide pool, visit, and group/treatment arm.
- Response rate and/or response magnitude comparisons of treatment arms as specified above.
- Response rate and/or response magnitude comparisons across time points as specified above.
- Listing of positive responders for cells expressing either IL-2 and/or IFN- γ based on the criteria used for the response rate table.

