Binding Antibody Multiplex Assay (BAMA) testing will be performed on serum samples from each participant in the protocol at visit 2 (month 0, baseline), visit 10 (month 6.5, 2 weeks post the 4th vaccination), and visit 12 (month 12, 6 months post the 4th vaccination). Specimens from other timepoints as well as other HIV antigens and antibody isotypes may be assayed based on the results of the initial assay. If sufficient immunogenicity is observed for the primary analysis antigens, additional assays will be performed using the exploratory antigens.

The following table lists the antigens for the analysis.

Panel	Antigen	Clade	Endpoint
Vaccine gp120 panel	1086C_D7gp120.avi/293F	C	Primary objective 3
	96ZM651.D11gp120.avi	C	Primary objective 3
	TV1c8_D11gp120.avi/293F	C	Primary objective 3
Vaccine V1V2 panel	C.1086C_V1_V2 Tags	C	Secondary objective 1
	gp70-96ZM651.02 V1v2	C	Secondary objective 1
	gp70-TV1.21 V1V2	C	Secondary objective 1
	gp70-TV1.GSKvacV1V2/293F	C	Secondary objective 1
Other V1V2	gp70_B.CaseA_V1_V2	B	Exploratory objective
	gp70_B.CaseA2_V1/V2/169K	B	Exploratory objective
Conensus gp140/gp120	Con 6 gp120/B	M	Exploratory objective
	Con S gp140 CFI	M	Exploratory objective
Other gp140	00MSA 4076 gp140	A	Exploratory objective
	A1.con.env03 140 CF	A	Exploratory objective
gp41	gp41	B	Exploratory objective

MFI will be employed for this essay. The frequency of positive responders (% responders) will be tabulated to access HIV binding antibody responses between placebo and vaccine groups from MFI readouts.

Samples from post-enrollment visits are declared to have a positive response if they meet three conditions:

1. The Net MFI (MFI*, i.e., MFI minus Blank values, where 'Blank value' refers to a plate-specific background measure) were \geq antigen-specific cutoff (based on the 95th percentile of the baseline samples).
2. The MFI* values were greater than 3 times the baseline MFI*.
3. The MFI values are greater than 3 times the baseline MFI values.

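### Does the missing multiplicity rule for ICS peptide-pool positivity calls leave the CD4+ primary endpoint open?

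*SAP*

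**What the plan says.** Section 4 declines adjustment across safety endpoints, primary immunogenicity endpoints and secondary endpoints. It then makes an exception: "multiplicity adjustments will be made for certain immunogenicity assays, as specified in the SAP". The exception applies where an assay endpoint is a collection of hypotheses, and the example is "testing multiple peptide pools to determine a positive response".

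Section 6.1 lists six peptide pools, among them TV1 gp120 and 1086 gp120. Fisher criteria serve until all samples have been assayed. From then on, "After, MIMOSA criteria will be used for positivity calls". A gene counts as positive if any of its pools is positive, and at the top level "If any peptide pool is positive, then the overall response to HIV-1 (Any HIV) for that T-cell subset is considered positive". For the comparisons between groups and timepoints, "Statistical tests with an unadjusted p-value ≤ 0.05 will be considered statistically significant". The output list in 6.1.1 allows "exact test criteria and/or MIMOSA criteria".

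Section 4.4.1 tests the CD4+ rates for TV1 and 1086 by two-sided Barnard's test at 0.05 and adds that "No adjustment will be made to the vaccine group estimates for the false positive rates in the placebo group".

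**The concern.** The SAP refers to itself for a rule that it does not contain. ICS is the only assay in it that uses peptide pools, so section 6.1 is where the rule should stand. That section is not pending: the revision table in section 8 shows it was added in version 1.1, whereas the neutralizing antibody section (6.2) is openly left to be completed. The four references cover neither Fisher nor MIMOSA calls. The binding antibody section (6.3) shows that the SAP can state a call rule in full: "Samples from post-enrollment visits are declared to have a positive response if they meet three conditions".

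Primary endpoint 2 is a response rate, so it depends on who is called a responder. If the adjustment runs over all six pools in a sample, applying or omitting it changes the TV1 and 1086 calls, and two analysts could reach different p-values from the same wells. If it does not, an unadjusted any-pool rule could still inflate Any HIV, and false positives would stay in the reported rate because no placebo correction is made.

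**Working it through.** The SAP gives no figure for this point, so there is none to reproduce. The check has two parts: which calls the promise reaches, and what either reading would do.

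**1. Which calls are affected**

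- Section 4 confines adjustment to endpoints made up of several hypotheses. Section 6.1 lists TV1 and 1086 as one pool each, and section 4.4.1 tests them individually. A single-pool call is not a union of pools; the gene-level and Any HIV calls are. The adjustment reaches TV1 and 1086 only if it spans all pools within a sample, which the SAP does not say.
- Section 4.5.2 runs the primary CD4+ analysis once all month 6.5 samples have been analysed. Section 6.1 moves to MIMOSA once all assays are complete. Together they make the primary calls MIMOSA calls. The looser wording in 6.1.1 describes what tables may show and need not override that sequence.

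**2. Union calls (Any HIV)**

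With six independent pools, each with false-positive rate a, the chance of at least one false call is 1 − (1 − a)^6:

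| a | any of six |
|---|---|
| 0.05 | 26.5% |
| 0.05/6 = 0.0083 | 4.9% |
| 0.01 | 5.9% |
| 0.001 | 0.6% |

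A simulation with one shared negative control and one-sided Fisher calls (assumed 50,000 to 200,000 cells per pool, background 0.01-0.05%) gives lower values: 13-19% unadjusted against 2-4% with Bonferroni over six pools at 0.05; 3-4% against 0.5-0.8% at 0.01; and 0.5% or less either way at 0.001. The size depends on a threshold that has to be assumed.

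**3. TV1 and 1086, if the adjustment did span six pools**

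The planning rates in section 1.5 are 49% against 69% (TV1) and 40% against 60% (1086). The same Fisher model, with lognormal net responses (log10 SD 0.4-0.7), assumed thresholds from 0.05 to 0.00001 and unadjusted rates set to the planning values, gives the following when the threshold is divided by six:

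| Antigen | MF59 | AS01B |
|---|---|---|
| TV1 | 32.6-46.5% | 54.1-66.9% |
| 1086 | 24.1-37.7% | 44.0-57.7% |

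Rates fall in both arms. The differences are 19.8 to 21.8 points, against 20 in the plan. Single-antigen Barnard power without and with adjustment is 45% and 44-49% (TV1, 42 per group), and 72% and 73-78% (1086, 85 per group). One-sided error per antigen is 0.019 to 0.025 under either reading.

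**4. False-positive calls in a single pool**

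If a fraction f of true non-responders is called positive, the observed rate is p + (1 − p)f, and a 20-point difference becomes 20 × (1 − f). At f = 0.05, TV1 goes from 49%/69% to 51.5%/70.5%, and exact one-sided Fisher power at 0.025 with 50 per group goes from 46.3% to 42.3%. At f = 0.0083 the difference is 19.8 points and power is 45.6%. With 100 per group the f = 0.05 case goes from 79.1% to 74.9%. The loss is modest and pulls the comparison towards no difference.

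**The case for a change.** The strongest case for a change is reproducibility. In the Fisher model, the Barnard verdict on an antigen differs between the two readings in 8-25% of simulated trials with 42 to 85 per group, although the average difference does not move. If the more favourable reading were picked after seeing results, one-sided error per antigen would rise to 0.026-0.040. The sentence on unadjusted p-values does not settle the matter, because it concerns comparisons between groups and timepoints, not calls on wells.

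The textual part stands: the cross-reference is empty, and the call threshold is unstated for both methods. The numerical part does not carry over to primary endpoint 2. Those figures describe Fisher calls adjusted over six pools, whereas the primary calls are MIMOSA calls on single pools, with no threshold in the SAP to simulate. Cell counts, background, spread and threshold are all assumed. The model also takes the planning rates as unadjusted, and section 1.5 does not say whether the earlier trial's calls were adjusted; if they were, the falls in part 3 do not follow. The 0.026-0.040 range further requires choosing between readings after the fact, which the SAP nowhere permits.

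The contrast with binding antibody is partial. The ADCC sections (6.4 and 6.5) also list response rates without a call rule, and section 6.2 shows that assay detail arrives through laboratory study plans. Whether the named criteria already contain an adjustment cannot be judged from this document.

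**Conclusion.** The gap is real but is one of documentation. Section 4 points to a rule that section 6.1 does not state. Filling it means recording the threshold and pool handling already in use, or dropping one sentence; it would not alter an analysis that the plan gets wrong. One positivity rule applies to all arms. Even on the least favourable reading tested, the group difference stays at about 20 to 22 points and one-sided error at 0.019 to 0.025 per antigen. The Any HIV inflation is sizeable only at a lax assumed cut-off and concerns a readout outside the two primary criteria in section 1.5. The placebo remark in section 4.4.1 does not bear on AS01B against MF59.

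This rests on reading sections 4.5.2 and 6.1 together, so that MIMOSA calls define primary endpoint 2, and on the same call rule being used in every arm. The Fisher-scale figures are illustrations under assumed inputs and should not be read as estimates for the primary endpoint. No change to the plan follows.

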4.1 Analysis variables

The analysis variables consist of baseline participant characteristics, safety, and immunogenicity for primary and secondary objective analyses.

4.2 Baseline comparability

Treatment groups will be compared for baseline participant characteristics using descriptive statistics.

4.3 Safety/tolerability analysis

Since enrollment is concurrent with receiving the first vaccination, all participants will have received at least 1 vaccination and therefore will provide some safety data.

4.3.1 Reactogenicity

The number and percentage of participants experiencing each type of reactogenicity sign or symptom will be tabulated by severity and treatment group and the percentages displayed graphically by group. For a given sign or symptom, each participant's reactogenicity will be counted once under the maximum severity for all injection visits. In addition to the individual types of events, the maximum severity of local pain or tenderness, induration or erythema, and of

systemic symptoms will be calculated. Kruskal-Wallis tests will be used to test for differences in severity between groups.

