1.2. Study Objectives and Endpoints

Primary objectives and endpoints

Primary objective 1

- To evaluate the safety and tolerability of ALVAC-HIV and bivalent gp120 protein/MF59 or bivalent gp120 protein/AS01_B.

Primary endpoints 1

- Severe local and systemic reactogenicity signs and symptoms (pain, tenderness, erythema, induration, fever, malaise/fatigue, myalgia, headache, nausea, vomiting, chills, arthralgia) up to 7 days after each vaccine dose
- AEs by body system, Medical Dictionary for Regulatory Activities (MedDRA) preferred term, severity, and assessed relationship to study products up to 30 days after each vaccine dose
- SAEs, AESIs, and new chronic conditions (requiring medical intervention for ≥ 30 days) throughout the study
- Laboratory measures: white blood cells (WBC), neutrophils, lymphocytes, hemoglobin, platelets, alanine aminotransferase (ALT), aspartate aminotransferase (AST), alkaline phosphate (ALP), and creatinine at baseline and following vaccinations
- AEs leading to early participant withdrawal or early discontinuation of study products administration throughout the study.

Primary objective 2

- To compare HIV-specific CD4+ T-cell response rates at the month 6.5 timepoint (2 weeks after the fourth vaccination) of ALVAC-HIV and bivalent gp120 protein/MF59 to each of the bivalent gp120 protein/AS01_B vaccine regimens.

Primary endpoint 2

- HIV-specific CD4+ T-cell response rates as assessed by flow cytometry.

Primary objective 3

- To compare HIV-specific Env-gp120 binding antibody response magnitudes at the month 12 timepoint (6 months after the fourth vaccination) of ALVAC-HIV and bivalent gp120 protein/MF59 to each of the bivalent gp120 protein/AS01_B vaccine regimens.

Primary endpoint 3

- HIV-specific Env-gp120 binding antibody response magnitude as assessed by multiplex assay.

Secondary objectives and endpoints

Secondary objective 1

- To further evaluate the systemic immune responses and the durability of immunogenicity of each vaccine regimen at the month 6.5 and month 12 timepoints.

Secondary endpoint 1

- HIV-specific total IgG binding antibody response breadth and magnitude as assessed by multiplex assay.
- Anti –V1/V2 scaffold IgG binding antibody responses as assessed by multiplex assay.
- HIV-specific CD4+ and CD8+ T-cell responses as assessed by flow cytometry.
- Additional immunogenicity assays may be performed on blood samples based on the HVTN Laboratory Assay Algorithm

Exploratory objectives

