1.5. Sample Size and Power

Safety

The goal of the safety evaluation for this study is to identify safety concerns associated with product administration. The ability of the study to detect SAEs can be expressed by the true event rate above which at least 1 SAE would likely be observed and the true event rate below which no events would likely be observed. Specifically, for each vaccine group of the study ($n=100$), there is a 90% chance of observing at least 1 event if the true rate of such an event is 2.3% or more; and there is a 90% chance of observing no events if the true rate is 0.1% or less.

Probabilities of observing 0, 1 or more, and 2 or more events among groups of size 100 are presented in Table 6-1 of the Protocol for a range of possible true adverse event rates. These calculations provide a more complete picture of the sensitivity of this study design to identify potential safety problems with a vaccine regimen.

An alternative way of describing the statistical properties of the study design is in terms of the 95% confidence interval (CI) for the true rate of an adverse event based on the observed data. Table 6-2 in the Protocol shows the 2-sided 95% CIs for the probability of an event based on a particular observed rate. Calculations are done using the score test method [1]. If none of the 100 participants receiving a vaccine regimen experience a safety event, the 95% 2-sided upper confidence bound for the true rate for such an event is 3.7%.

Immunogenicity

The primary immunogenicity evaluation is to compare Groups 2 and 3 (AS01B groups) separately to Group 1 (MF59 group) based on the following two criteria:

1. Establish superiority of the AS01B regimen in CD4+ T-cell response rate at month 6.5 for either TV1 or 1086; AND
2. Establish superiority of the AS01B regimen in magnitude of anti-gp120 antibody response at month 12 for 1086.

Power is calculated for each group comparison separately and assumes that:

1. The CD4+ T-cell response rate for the AS01B regimen is at least 20% higher for both antigens; AND,
2. The true geometric mean anti-gp120 binding antibody response is 1.5-fold higher for the AS01B regimen.

Power is based on data simulations using HVTN 100 CD4+ T-cell data from the month 6.5 visit (2 weeks after the fourth vaccination) and predicted anti-gp120 1086 antibody binding magnitude

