4.3.2 AEs and SAEs

AEs will be summarized using MedDRA System Organ Class and preferred terms. Tables will show by treatment group the number and percentage of participants experiencing an AE within a System Organ Class or within preferred term category by severity or by relationship to study product. For the calculations in these tables, a participant with multiple AEs within a category will be counted once under the maximum severity or the strongest recorded causal relationship to study product. Formal statistical testing comparing groups is not planned since interpretation of differences must rely heavily upon clinical judgment.

A listing of SAEs reported to the DAIDS Regulatory Support Center (RSC) Safety Office will provide details of the events including severity, relationship to study product, time between onset and last vaccination, and number of vaccinations received. A separate listing will do the same for AEs of special interest (AESI). AESI for this protocol include but are not limited to potential immune-mediated disorders; a sample list of AESI is provided in Appendix H of the Protocol. These listings will be submitted to the FDA in all annual reports and clinical trial reports.

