5.2 Participant Listings

The following listings of participant-level data are included in the SMB reports.

- Discontinuations
- Pregnancies
- Severe or Life-Threatening Local and Systemic Reactogenicities
- Moderate or Severe Erythema and Induration
- Expedited Adverse Experiences (EAEs)
- Adverse Experiences of Special Interest (AESIs)
- Severe, Life-Threatening, or Fatal Adverse Experiences
- Study Product Administration Errors

- HIV Infection Results from Lab and Reported by Site

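### Reactogenicity endpoint counts severe reactions, but the only planned test compares all severity grades, and no interval or group contrast is planned for the severe proportion

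*SAP*

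**What the plan says.** Under primary endpoints 1, SAP section 1.2 lists "Severe local and systemic reactogenicity signs and symptoms" in the 7 days after each dose. It is the first of five safety items.

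Section 4.3.1 describes the analysis. Counts and percentages are to be shown per grade and group, in tables and graphs. The variable is a maximum grade: "each participant's reactogenicity will be counted once under the maximum severity for all injection visits". A maximum is also taken over the local and over the systemic items. The test is then named: "Kruskal-Wallis tests will be used to test for differences in severity between groups". No cut at severe is made, and neither the groups entering the test nor its alpha level is stated.

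This is the only named test in section 4.3. For adverse events, section 4.3.2 says: "Formal statistical testing comparing groups is not planned since interpretation of differences must rely heavily upon clinical judgment". Sections 4.3.3 and 4.3.4 (laboratory values, discontinuations) are descriptive.

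Section 5.2 adds a participant listing of "Severe or Life-Threatening Local and Systemic Reactogenicities" to the safety monitoring board reports. Section 1.5 describes safety precision through the "95% confidence interval (CI) for the true rate of an adverse event based on the observed data", calculated by the score method, and section 4.4.1 applies the same method to immune response rates. Section 4.3 plans no such interval for severe reactions.

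**The concern.** The endpoint as defined asks what proportion of participants have a severe reaction and whether it differs between regimens. The Kruskal-Wallis null is that the whole distribution over none, mild, moderate and severe is the same in the groups. If severe is a small category, the ranks are governed mainly by how participants divide among the lower grades. The test can therefore respond when severe rates are equal, and stay quiet when only the severe rate differs.

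At stake is how the reactogenicity tables are read when AS01B is compared with MF59. The severe percentages will carry no measure of uncertainty, and the one p-value beside them answers a broader question. A significant result may reflect only mild or moderate reactions. A non-significant one does not rule out an excess of severe reactions.

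**Working it through.** **1. The SAP's own safety figures.** Section 1.5 uses 100 per vaccine group.
- Chance of at least 1 event at a true rate of 2.3%: 1 − 0.977^100 = 90.2% (stated 90%).
- Chance of no event at 0.1%: 0.999^100 = 90.5% (stated 90%).
- Score upper bound for 0/100, with z² = 3.84: z²/(n + z²) = 3.84/103.84 = 3.7% (stated 3.7%).

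All three reproduce. Table 3-1 shows 50 per vaccine group, where the first figure would be 1 − 0.977^50 = 68.8% and the upper bound 3.84/53.84 = 7.1%. That the two group sizes differ is a separate matter to reconcile; results below are for 50, with some for 100. The SAP states no power for the Kruskal-Wallis test.

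**2. Assumptions for the simulation.** None of these stands in the SAP: Group 1 grades none/mild/moderate/severe = 30/45/20/5%; Groups 2 and 3 alike; Groups 1 to 3 in the test; alpha 0.05. There were 3,000 trials per scenario. The comparator is a three-group Pearson chi-square on severe yes/no.

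**3. Validity.** With identical grades in all three groups and 50 per group, Kruskal-Wallis rejects 4.9% and the severe-only test 4.0%. The test is sound for its own null.

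**4. Equal severe rates (5% everywhere), different lower grades.**

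| Groups 2 and 3 (none/mild/moderate/severe) | n per group | Kruskal-Wallis | Severe-only |
|---|---|---|---|
| 20/40/35/5% | 50 | 35% | 4% |
| 15/40/40/5% | 50 | 62% | 4% |
| 15/40/40/5% | 100 | 92% | 4% |

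With another assumed reference (20/50/26/4%, moderate 26% v 46%, severe 4% throughout, 50 per group), Kruskal-Wallis rejected between 29% and 57%, depending on which lower grades the extra moderate reactions came from.

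**5. Different severe rates, 50 per group.** Three patterns for the excess over 5%:
- *From moderate only*: at 15% severe the grades are 30/45/10/15%.
- *Proportional*: the lower grades are multiplied by 0.85/0.95, giving 26.8/40.3/17.9/15%.
- *Proportional odds*: all cumulative odds are multiplied by (0.15/0.85)/(0.05/0.95) = 3.35, giving 11.3/35.9/37.8/15%.

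| Severe, Group 1 v Groups 2 and 3 | Pattern | Kruskal-Wallis | Severe-only |
|---|---|---|---|
| 5% v 15% | from moderate only | 5% | 37% |
| 5% v 15% | proportional | 14% | 35% |
| 5% v 15% | proportional odds | 93% | 36% |
| 5% v 20% | from moderate only | 6% | 64% |
| 5% v 20% | proportional | 28% | 62% |
| 5% v 20% | proportional odds | 99.6% | 65% |

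The severe-only column depends almost entirely on the severe rates. The Kruskal-Wallis column depends on what the lower grades do.

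**6. Precision of the missing interval.** The score interval for x/n with p = x/n has centre (p + z²/2n)/(1 + z²/n) and half-width z√(p(1−p)/n + z²/4n²)/(1 + z²/n).
- 0/50: 0 to 7.1%.
- 2/50: centre (0.04 + 0.0384)/1.0768 = 0.0728; half-width 1.96 × √(0.000768 + 0.000384)/1.0768 = 0.0618; interval 1.1% to 13.5%.

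**The case against.** The strongest case for the plan has four parts.

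- **Kruskal-Wallis may be the better detector.** A reader might infer from the severe-only patterns that the test misses most real differences in severe reactions. The SAP does not support that. If a more reactogenic adjuvant raises every grade together, Kruskal-Wallis has 93% power against 36% for a severe-only test at 5% v 15%. The SAP gives no grade rates by which to choose between patterns, so no single miss rate can be derived. This part stands in full.
- **Low power is partly a matter of group size.** At 5% v 10% with 50 per group, a severe-only test reaches only about 13% to 14%. Replacing one p-value with another would not give assurance about severe reactions. This stands, and is why the remedy is an estimate with an interval rather than another test.
- **The 62% is not a false-positive rate.** Moderate reactions do differ in that scenario, and the test detects the difference in severity it is meant to detect. Objective 1 also covers tolerability, to which all grades are relevant. This stands; the problem is only what the result can be taken to say about severe reactions.
- **Severe reactions are already reported, and nothing makes Kruskal-Wallis the safety decision.** Percentages by grade and group are tabulated, severe cases are listed, and section 1.5 states no between-group safety hypothesis. It would go too far to say that the endpoint goes unreported or that this p-value is its designated verdict. But a percentage without an interval conveys no uncertainty, and the only inferential output is aimed at a different quantity.

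**Conclusion.** The concern holds as a mismatch between endpoint and analysis: the endpoint is severe reactions, the only test in section 4.3 uses all grades, and the severe proportion has neither an interval nor a group contrast. A significant Kruskal-Wallis result does not show a difference in severe reactions, and a non-significant one does not exclude it.

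The size depends on assumed grade rates. With 50 per group and Groups 1 to 3 in the test, rejection with equal severe rates was 29% to 62% where moderate reactions differed by 20 percentage points. Power at severe 5% v 15% ran from 5% to 93% according to the pattern in the lower grades. That spread is itself the finding: the p-value cannot be interpreted for severe reactions without knowing what the other grades did. The test is valid for overall severity and worth keeping for that purpose. The change should be made, but it is an addition to reporting and does not overturn the safety plan.

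**What to change.** In section 4.3.1:

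1. For each group, report the number and proportion of participants with a severe or worse reaction, for any local and any systemic reaction, with the 95% score interval already named in sections 1.5 and 4.4.1.
2. Report the difference in that proportion for Group 2 v Group 1 and Group 3 v Group 1, each with a 95% interval. Present these as estimates, without added per-symptom tests; those would be many sparse comparisons, and section 4 plans no multiplicity adjustment for safety.
3. Describe Kruskal-Wallis as a supportive comparison of severity over all grades, and state that it is not evidence for or against a difference in severe reactions.

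The cost is a few sentences in the SAP and some extra columns in the existing maximum reactogenicity tables, with no new data. The intervals will be wide at 50 per group, but that width tells the reader how little a low or zero count excludes.
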